5.3. Other Considerations for Data Analyses and Data Handling Conventions

Other considerations for data analyses and data handling conventions are outlined in the appendices:

Section	Component
13.3	Appendix 3: Assessment Windows
13.4	Appendix 4: Study Phases and Treatment Emergent Adverse Events
13.5	Appendix 5: Data Display Standards & Handling Conventions
13.6	Appendix 6: Derived and Transformed Data
13.7	Appendix 7: Reporting Standards for Missing Data
13.8	Appendix 8: Values of Potential Clinical Importance

6. STUDY POPULATION ANALYSES

6.1. Overview of Planned Study Population Analyses

The study population analyses will be based on the randomised population, unless otherwise specified.

Study population analyses including analyses of subject's disposition, protocol deviations, demographic and baseline characteristics, prior and concomitant medications, and exposure and treatment compliance will be based on GSK Core Data Standards. Details of the planned displays are presented in [Appendix 12: List of Data Displays](#).

7. SAFETY ANALYSES

The safety analyses will be based on the safety population, unless otherwise specified.

Descriptive statistics will be used to assess safety and tolerability objectives. No formal statistical analyses of safety data are planned. Data will be summarized according to GSK Integrated Data Standards Library (IDSL) standards for Part A, Part B and Part C separately. In addition, individual participant data will be reviewed. Treatment comparisons with placebo will be based on review of descriptive statistics and individual participant data.

7.1. Adverse Events Analyses

Adverse events analyses including the analysis of adverse events (AEs), Serious adverse events (SAEs) and other significant AEs will be based on GSK Core Data Standards.

7.2. Clinical Laboratory Analyses

Laboratory evaluations including the analyses of Chemistry laboratory tests, Hematology laboratory tests, Urinalysis, Liver chemistries and Hormone assessment tests will be based on GSK Core Data Standards. Hormone assessment tests will be done in Part B only and all the other laboratory evaluations will be done for all the 3 parts (A, B & C) of the study.

7.3. Other Safety Analyses

The analyses of non-laboratory safety test results including ECGs vital signs and Telemetry will be based on GSK Core Data Standards, unless otherwise specified.

8. PHARMACOKINETIC ANALYSES

8.1. Primary Pharmacokinetic Analyses

8.1.1. Endpoint / Variables

Pharmacokinetic parameters will be determined from the plasma concentration-time data, as data permits.

PK parameters: Maximum observed blood concentration (C_{max}), time to C_{max} (t_{max}), area under the plasma concentration-time curve [$AUC(0-t)$, $AUC(0-24)$, $AUC(0-inf)$ and $AUC(0-\tau)$], Pre-dose observed concentration (C_{τ}), apparent terminal phase half-life ($t_{1/2}$) will be determined, as data permit.

8.1.1.1. Drug Concentration Measures

Refer to [Appendix 5: Data Display Standards & Handling Conventions \(Section 13.5.3. Reporting Standards for Pharmacokinetic\)](#)

8.1.1.2. Derived Pharmacokinetic Parameters

Pharmacokinetic parameters will be calculated by standard non-compartmental analysis according to current working practices and using Phoenix 64. All calculations of non-compartmental parameters will be based on actual sampling times. Pharmacokinetic parameters listed will be determined from the plasma concentration-time data, as data permits.

Table 2 Derived Pharmacokinetic Parameters (Primary end points)

Parameter	Parameter Description	Part A	Part B	Part C
AUC(0-t)	Area under the concentration-time curve from time zero to the time of the last quantifiable concentration ($C(t)$) which will be calculated using the linear trapezoidal rule for each incremental trapezoid and the log trapezoidal rule for each decremental trapezoid.	X	X ¹	X
AUC(0-∞)	Area under the concentration-time curve extrapolated to infinity calculated as $AUC(0-\infty) = AUC(0-t) + C(t)/\lambda_z$	X	X ¹	X
AUC(0-24)	Area under the concentration-time curve from time zero to 24 hours post-dose which will be calculated using the linear trapezoidal rule for each incremental trapezoid and the log trapezoidal rule for each decremental trapezoid.	X	X ^{1,2}	

Parameter	Parameter Description	Part A	Part B	Part C
t _{max}	Time to reach C _{max} , determined directly from the concentration-time data.	X	X ^{1,2}	X
t _{1/2}	Apparent terminal half-life will be calculated as: $t_{1/2} = \ln 2 / \lambda_z$	X	X ^{1,2}	X
A _e	Urinary excretion of unchanged drug		X ^{1,2}	
Cl _r	Renal clearance		X ^{1,2}	
F _e	Fraction of the dose excreted in the urine		X ^{1,2}	
C _{max}	Maximum observed concentration, determined directly from the concentration-time data.	X	X ^{1,2}	X
C _τ	Pre-dose observed concentration (trough) for repeat doses on Days 6,7,9,10, 11, 15,16, and 17 (6, 7, 9 & 10 for 7 day repeat dosing) which will be obtained directly from the concentration-time data.		X ^{1,2}	

Additional parameters may be calculated as required.

λ_z is the terminal phase rate constant.

¹Determined for dose 1

²Determined at SS (following 14 days of consecutive dosing)

8.1.2. Summary Measure

Pharmacokinetic data will be presented in graphical and/or tabular form and will be summarized descriptively by dose group for each study part separately.

Refer to [Appendix 5: Data Display Standards & Handling Conventions \(Section 13.5.3. Reporting Standards for Pharmacokinetic\)](#)

Pharmacokinetic analysis will be the responsibility of the Clinical Pharmacology Modelling and Simulation Department, CPMS, GlaxoSmithKline and Statistical analyses of the pharmacokinetic parameter data will be the responsibility of Clinical Statistics & Programming, GlaxoSmithKline.

8.1.3. Population of Interest

The primary pharmacokinetic analyses will be based on the Pharmacokinetic population, unless otherwise specified.

8.2. Secondary Pharmacokinetic Analyses

8.2.1. Endpoint / Variables

Observed accumulation ratio AUC(R_o), predicted accumulation ratio AUC(R_p), observed accumulation ratio for C_{max} (R_{Cmax}) and steady state ratio (R_{ss}).

8.2.1.1. Drug Concentration Measures

Refer to [Appendix 5: Data Display Standards & Handling Conventions \(Section 13.5.3 Reporting Standards for Pharmacokinetic\)](#)

8.2.1.2. Derived Pharmacokinetic Parameters

Table 3 Derived Pharmacokinetic Parameters (Secondary end points)

Parameter	Parameter Description	Part A	Part B	Part C
% AUC _{ex}	The percentage of AUC (0-∞) obtained by extrapolation (%AUC _{ex}) will be calculated as: $AUC(0-\infty) - AUC(0-t) / AUC(0-\infty) \times 100$	X	X	X
AUC(R _o)	Observed accumulation ratio (R _o) for AUC will be calculated as follows: Day 17 AUC(0-τ)/Day 1 AUC(0-τ)		X ¹	
AUC(R _p)	Predicted accumulation ratio will be calculated as follows: Day 1 AUC(0-∞)/Day 1 AUC(0-24)	X	X ¹	X
R _{ss}	Steady state accumulation ratio (R _{ss}) will be calculated as follows: Day 17 AUC(0-τ)/Day 1 AUC(0-∞)		X ¹	
RC _{max}	Observed accumulation ratio for C _{max} (RC _{max}) will be calculated as follows: Day 17 C _{max} /Day 1 C _{max}		X ¹	

¹Day 10 AUC will be considered instead of Day 17 for the reduced treatment period cohort (Part B cohort3).

8.2.2. Summary Measure

Refer to [Appendix 5: Data Display Standards & Handling Conventions \(Section 13.5.2. Reporting Standards for Pharmacokinetic\)](#)

8.2.3. Population of Interest

The secondary pharmacokinetic analyses will be based on the Pharmacokinetic population, unless otherwise specified.

8.2.4. Statistical Analyses / Methods

Details of the planned displays are provided in [Appendix 12: List of Data Displays](#) and will be based on GSK Data Standards and statistical principles.

Unless otherwise specified, endpoints / variables defined in Section 8.2.1.2 will be summarised using descriptive statistics, graphically presented (where appropriate) and listed.

8.2.4.1. Statistical Methodology Specification**8.2.4.1.1. Statistical Methodology Specification for Part A (Single Dose)**

Pharmacokinetic Statistical Analyses – ANOVA – Single Dose (Part A)
Endpoint / Variables
AUC(0-t), AUC(0-24), AUC(0-∞), C _{max} , C _τ , t _{1/2} , AUC(R _p)
Model Specification

Actual value of t_{1/2} and loge-transformed values of rest of the endpoints will be statistically analyzed using Mixed Model (MM) ANOVA.
 
 • Fixed effect: dose • Random effect: Subject 
An unstructured covariance structure for the G matrix will be used.
 
 • If this model fails to converge, alternative covariance structures may be considered. • Akaike's Information Criteria (AIC) will be used to assist with the selection of covariance structure. 
Analyses will be done with the MIXED Procedure in SAS, using the Kenward-Roger option to estimate denominator degrees of freedom and standard errors

Model Checking & Diagnostics

 • For the Mixed Model, model assumptions will be checked, and appropriate adjustments may be applied based on the data. • Distributional assumptions underlying the model used for analysis will be examined by obtaining a normal probability plot of the residuals and a plot of the residuals versus the fitted values (i.e. checking the normality assumption and constant variance assumption of the model respectively) to gain confidence that the model assumptions are reasonable. • If there are any departures from the distributional assumptions, alternative transformations, such as data squared or square root of data, will be explored. • Non-parametric analyses will be conducted if the normality assumption does not hold.
Model Results Presentation

LSmeans and 90% CI are estimated for each dose as well as overall estimate of within-subject CV
 
Note: AUC(0-t) is only reported when AUC(0-∞) is not reportable

Pharmacokinetic Statistical Analyses - Dose Proportionality (Power Model) – Single Dose (Part A)
Endpoint / Variables
Single Dose: AUC(0-t), AUC(0-∞) and C _{max}
Model Specification

Will be statistically analyzed using the power model
 $y = \alpha^* \text{dose}^\beta$

Where y = PK parameter being analyzed and α = subject

Loge transformed data will be analyzed by fitting the following terms in the mixed effect model:

- Fixed effect: loge (dose)
- Random effect: Subject (Intercept only)

Model Checking & Diagnostics

- For the Mixed Model, model assumptions will be checked, and appropriate adjustments may be applied based on the data.
- Distributional assumptions underlying the model used for analysis will be examined by obtaining a normal probability plot of the residuals and a plot of the residuals versus the fitted values (i.e. checking the normality assumption and constant variance assumption of the model respectively) to gain confidence that the model assumptions are reasonable.
- If there are any departures from the distributional assumptions, alternative transformations, such as data squared or square root of data, will be explored.
- Non-parametric analyses will be conducted if the normality assumption does not hold.

Model Results Presentation

Estimates of the mean slopes of \log_e (dose) will be reported along with corresponding 90% confidence intervals (slope \approx 1 implies dose proportionality)

Note: AUC(0-t) is only reported when AUC(0- ∞) is not reportable

8.2.4.1.2. Statistical Methodology Specification for Part B

Pharmacokinetic Statistical Analyses – ANOVA (Accumulation & Time Invariance) – Repeat Dose (Part B)

Endpoint / Variables

AUC(0- τ), AUC(0- ∞), C_{max}, C_T, AUC R_{ss}, t_{1/2}, AUC (R_o), RC_{max}

Model Specification

Actual value of t_{1/2} and loge-transformed values of all other will be statistically analyzed using Mixed Model (MM) ANOVA.

- Fixed effect: day, dose, day*dose
- Random effect: Subject

An unstructured covariance structure for the G matrix will be used.

- If this model fails to converge, alternative covariance structures may be considered.
- Akaike's Information Criteria (AIC) will be used to assist with the selection of covariance structure.

Analyses will be done with the MIXED Procedure in SAS, using the Kenward-Roger option to estimate denominator degrees of freedom and standard errors

Model Checking & Diagnostics

 For the Mixed Model, model assumptions will be checked, and appropriate adjustments may be applied based on the data. Distributional assumptions underlying the model used for analysis will be examined by obtaining a normal probability plot of the residuals and a plot of the residuals versus the fitted values (i.e. checking the normality assumption and constant variance assumption of the model respectively) to gain confidence that the model assumptions are reasonable. If there are any departures from the distributional assumptions, alternative transformations, such as data squared or square root of data, will be explored. Non-parametric analyses will be conducted if the normality assumption does not hold.
Model Results Presentation

LSmeans and 90% CI are estimated for each dose as well as overall estimate of within-subject CV. For AUC(0- τ), Cmax and AUC-Rss, estimates of ratio of Day 17 to Day 1 will be evaluated for each dose by exponentiating the difference in least squares means (Day 17– Day 1) and the associated 90% CI. Such that ratios of Day 17 to Day 1 for AUC(0- τ), Cmax and AUC-Rss provide estimates of Ro, RCmax and Rss, respectively
 
Note: For AUC-Rss, Day 17 AUC(0- τ) and Day 1 AUC(0-∞) should be considered.
 
Note: Day 10 values will be considered instead of Day 17 for the reduced treatment period cohort (cohort 3)

Pharmacokinetic Statistical Analyses - Dose Proportionality (Power Model) – Repeat Dose (Part B)
Endpoint / Variables
Repeat Dose: AUC(0- τ) and Cmax
Model Specification

Will be statistically analyzed using the power model
 $y = \alpha * \text{dose}^\beta$ 
Where y =PK parameter being analyzed and α= subject
 
Log_e transformed data will be analyzed by fitting the following terms in the mixed effect model:
 
 Fixed effect: log_e (dose) Random effect: Subject (Intercept only)
Model Checking & Diagnostics

 For the Mixed Model, model assumptions will be checked, and appropriate adjustments may be applied based on the data. Distributional assumptions underlying the model used for analysis will be examined by obtaining a normal probability plot of the residuals and a plot of the residuals versus the fitted values (i.e. checking the normality assumption and constant variance assumption of the model respectively) to gain confidence that the model assumptions are reasonable. If there are any departures from the distributional assumptions, alternative transformations, such as data squared or square root of data, will be explored.

 • Non-parametric analyses will be conducted if the normality assumption does not hold.
Model Results Presentation
Estimates of the mean slopes of \log_e (dose) will be reported along with corresponding 90% confidence intervals (slope \approx 1 implies dose proportionality)
Pharmacokinetic Statistical Analyses - Achievement of Steady State – Repeat Dose (Part B)
Endpoint / Variables
Trough plasma concentrations at the end of the dosing interval (C_{τ}) for repeat doses Days 6,7,9,10, 11, 15,16, and 17 (6, 7, 9 & 10 for reduced treatment period cohort)
Model Specification

\log_e-transformed values of the endpoint will be statistically analyzed separately by dose using Mixed Model (MM) ANOVA.
 
 • Fixed effect: day as continuous variable, dose, day*dose • Random effect: Subject 
An unstructured covariance structure for the G matrix will be used.
 
 • In the event that this model fails to converge, alternative covariance structures may be considered. • Akaike's Information Criteria (AIC) will be used to assist with the selection of covariance structure. 
Analyses will be done with the MIXED Procedure in SAS, using the Kenward-Roger option to estimate denominator degrees of freedom and standard errors

Model Checking & Diagnostics

 • For the Mixed Model, model assumptions will be checked, and appropriate adjustments may be applied based on the data. • Distributional assumptions underlying the model used for analysis will be examined by obtaining a normal probability plot of the residuals and a plot of the residuals versus the fitted values (i.e. checking the normality assumption and constant variance assumption of the model respectively) to gain confidence that the model assumptions are reasonable. • If there are any departures from the distributional assumptions, alternative transformations, such as data squared or square root of data, will be explored. • Non-parametric analyses will be conducted if the normality assumption does not hold.
Model Results Presentation

The coefficient for the slope of the day effect on the log-scale will be used to evaluate steady state for each dose. The 90% confidence intervals for the slope will be calculated.
 
Steady-state will be assessed visually by plotting trough concentration levels, C_{τ}, collected pre-morning dose versus collection day by dose.

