Procedure	Screening (up to 30 days before Day 1)	Intervention Period [Days] (for each dosing cohort)															E.D	Follow-up (~14±1 days post last dose)	Notes E.D = early discontinuation/withdrawal
		-2	-1	1	2	3	4	5	6	7	8	9	10	11	12	13			
Urine sampling PD			X ⁸	X ⁹						X ⁹				X ⁹				(X)	
⁸combined void for windows of 24-22 hr, 22-20 hr, 20-18 hr, 18-16 hr, 16-12 hr, and 12-0 hr predose.
 
⁹combined void for windows of 0-2 hr, 2-4 hr, 4-6 hr, 6-8 hr, 8-12 hr, and 12-24 hr post-dose
 
Aliquots will be removed prior to pooling for urine PK. Total urine volume will be recorded before aliquots for PD are removed.

Part B .2- 7 Day Repeat Dose																			
Procedure	Screening (up to 30 days before Day 1)	Intervention Period [Days] (for each dosing cohort)															E.D	Follow-up (~14±1 days post last dose)	Notes E.D = early discontinuation/withdrawal
		-2	-1	1	2	3	4	5	6	7	8	9	10	11	12	13			
24h urine sampling for PK and metabolite profiling			X	X										X			(X)	
Voids from urine pharmacodynamic (PD) sampling windows will be combined into 0-24 hr pools on Day -1, 1, and 10 after aliquoting for PD.
 
These voids will be combined for PK/metabolite analysis only after aliquots for urine PD are removed
 
See study reference manual (SRM) for details on samples and processing
	
Blood sampling for PK					X ¹⁰				X ¹¹	X ¹¹		X ¹¹		X ¹⁰			(X)	
¹⁰Day 1 and Day 10: Predose, 5 min, 30 min, 1 hr, 1.5hr, 2 hr, 3 hr, 4 hr, 6 hr, 8 hr, 10 hr, 12 hr, 18 hr, 24 hr, 36 hr, 48 hr, 60 hr, and 72 hr post-dose
 
¹¹pre-dose samples collected on days 6, 7, and 9
	

Part B .2- 7 Day Repeat Dose																			
Procedure	Screening (up to 30 days before Day 1)			Intervention Period [Days] (for each dosing cohort)													E.D	Follow-up (~14±1 days post last dose)	Notes E.D = early discontinuation/withdrawal
		-2	-1	1	2	3	4	5	6	7	8	9	10	11	12	13			
Blood sampling for metabolite profiling				X										X					Day 1 and Day 10 Predose, 5 min, 30 min, 1 hr, 1.5 hr, 2 hr, 3 hr, 4 hr, 6 hr, 8 hr, 10 hr, 12 hr, 18 hr, 24 hr, 36 hr, 48 hr, 60 hr, and 72 hr post-dose
Blood sampling for Pharmacodynamics and biomarkers				X ¹²	X ¹²					X ¹³			X ¹³				(X)	¹² Predose and 24 hr post-dose on Day 1 ¹³ Predose Days 7 and 10	

Part B .2- 7 Day Repeat Dose																			

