3. OBJECTIVES AND ENDPOINTS

Objectives	Endpoints

Primary
 
 • To assess the safety and tolerability of GSK3439171A following single and repeat doses in healthy participants • To characterize the PK of GSK3439171A, following single and repeat doses in healthy participants 	
 • Adverse events (AE), clinical laboratory values, vital signs, and electrocardiograms (ECG) • Derived PK parameters for GSK3439171A including area under the plasma drug concentration versus time curve (AUC(0-t), AUC(0-inf), maximum observed plasma drug concentration (C_{max}), time to maximum observed plasma drug concentration (t_{max}), and apparent terminal half-life ($t_{1/2}$) as appropriate

Secondary
 
 • To assess the effect of food on the PK of GSK3439171A following an oral dose in healthy participants • To assess preliminary dose proportionality of GSK3439171A 	
 • Derived PK parameters for GSK3439171A including area under the plasma drug concentration versus time curve (AUC(0-t), AUC(0-inf), maximum observed plasma drug concentration (C_{max}), time to maximum observed plasma drug concentration (t_{max}), and apparent terminal half-life ($t_{1/2}$) as appropriate • AUC(0-t), AUC(0-inf), and C_{max} following single dose and AUC(0-τ)

Objectives	Endpoints

following single and repeat oral doses, as data permit
 
 • To examine the extent of accumulation and achievement of steady-state following repeat oral doses of GSK3439171A, as data permits 	
and Cmax following repeat dose for the assessment of dose proportionality
 
 • Determine observed accumulation based on AUC(Ro) and Cmax (RCmax) and determine the steady-state ratio (Rss) • Trough plasma concentrations at the end of the dosing interval (C_T) collected pre-dose for repeat doses 3, 4, 12, 13 and 14 (repeat doses 3,4,6, and 7 for 7 day dosing) to assess the achievement of steady-state of GSK3439171A

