Achievement of Steady State (Part B: Repeat Dose Study Phase)

Steady-state will be assessed visually by plotting trough concentration levels, C_{τ} , collected pre-morning dose versus collection day by dose. In addition, statistical analysis of trough concentration levels (e.g., Days 6,7,9, and 10 (7 day repeat dosing period) or 6-7, 16-17 (14 day repeat dosing period) will be performed after log-transformation of the concentrations. A mixed effects ANOVA model will be fit with day (continuous variable) as a fixed effect and subject as a random effect for each dose level separately. The coefficient for the slope of the day effect on the log-scale will be used to evaluate steady state for each dose. The 90% confidence intervals for the slope will be calculated.

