Genetic sample				X															Any time predose on Day 1 This research may be described in a separate ICF or as part of a combined ICF. A separate signature is required where participant participation is optional		
Study intervention				X			←=====X=====→														
Telemetry				X															Telemetry performed starting 30 (±10 min) pre-dose to 12 hr (±20 min) post-dose		
AE review					←=====X=====→																
SAE review	←=====X=====→																				
Concomitant medication review	←=====X=====→																				

Part B .2- 7 Day Repeat Dose																			
Procedure	Screening (up to 30 days before Day 1)	Intervention Period [Days] (for each dosing cohort)															E.D	Follow-up (~14±1 days post last dose)	Notes E.D = early discontinuation/withdrawal
		-2	-1	1	2	3	4	5	6	7	8	9	10	11	12	13			
Urine sampling PD			X ⁸	X ⁹						X ⁹				X ⁹			(X)	
⁸combined void for windows of 24-22 hr, 22-20 hr, 20-18 hr, 18-16 hr, 16-12 hr, and 12-0 hr predose.
 
⁹combined void for windows of 0-2 hr, 2-4 hr, 4-6 hr, 6-8 hr, 8-12 hr, and 12-24 hr post-dose
 
Aliquots will be removed prior to pooling for urine PK. Total urine volume will be recorded before aliquots for PD are removed.
	

Part B .2- 7 Day Repeat Dose																			
Procedure	Screening (up to 30 days before Day 1)	Intervention Period [Days] (for each dosing cohort)															E.D	Follow-up (~14±1 days post last dose)	Notes E.D = early discontinuation/withdrawal
		-2	-1	1	2	3	4	5	6	7	8	9	10	11	12	13			
24h urine sampling for PK and metabolite profiling			X	X											X			(X)	
Voids from urine pharmacodynamic (PD) sampling windows will be combined into 0-24 hr pools on Day -1,1, and 10 after aliquoting for PD.
 
These voids will be combined for PK/metabolite analysis only after aliquots for urine PD are removed
 
See study reference manual (SRM) for details on samples and processing

Part B .2- 7 Day Repeat Dose																					
Procedure	Screening (up to 30 days before Day 1)			Intervention Period [Days] (for each dosing cohort)													E.D	Follow-up (~14±1 days post last dose)	Notes E.D = early discontinuation/withdrawal		
				-2	-1	1	2	3	4	5	6	7	8	9	10	11				12	13
Blood sampling for PK						X ¹⁰						X ¹¹	X ¹¹			X ¹¹		X ¹⁰	(X)	¹⁰ Day 1 and Day 10: Predose, 5 min, 30 min, 1 hr, 1.5hr, 2 hr, 3 hr, 4 hr, 6 hr, 8 hr, 10 hr, 12 hr, 18 hr, 24 hr, 36 hr, 48 hr, 60 hr, and 72 hr post-dose ¹¹ pre-dose samples collected on days 6, 7, and 9	

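### The steady-state slope omits the end-of-interval concentration after the last dose, although it is already collected; under once-daily dosing this can widen the 90% CI by up to about 31% (7-day cohort) or 15% (14-day cohorts).

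*SAP*

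**What the plan says.** SAP 8.2.4.1.2 (Achievement of Steady State, Part B) takes as its endpoint the trough at the end of the dosing interval, "for repeat doses Days 6,7,9,10, 11, 15,16, and 17", with "6, 7, 9 & 10 for reduced treatment period cohort". SAP Table 2 (8.1.1.2) narrows this to a pre-dose value: "Pre-dose observed concentration (trough) for repeat doses on Days 6,7,9,10, 11, 15,16, and 17". Protocol section 3 does the same, describing the trough as "collected pre-dose for repeat doses 3, 4, 12, 13 and 14".

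The model is linear in day: "Fixed effect: day as continuous variable, dose, day*dose" in the SAP, and in Protocol 9.4 day as a continuous effect with "subject as a random effect for each dose level separately". The slope and its 90% CI are reported for each dose, next to a plot of pre-morning-dose troughs. Neither document sets an acceptance margin for the slope.

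Protocol 4.1 starts repeat dosing on Day 4 and puts discharge on Day 13 or Day 20, three days after the last dose. The last dose is therefore on Day 10 (7-day cohort) or Day 17 (14-day cohorts). For the 7-day cohort the Schedule of Activities has "pre-dose samples collected on days 6, 7, and 9", plus a serial profile on Day 10 that runs through "10 hr, 12 hr, 18 hr, 24 hr, 36 hr, 48 hr, 60 hr, and 72 hr post-dose". The 14-day schedule has the same profile on Day 17. Protocol 6.3.1 leaves the Part B regimen open between once and twice daily.

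**The concern.** The pre-dose sample on the last dosing day closes the interval of repeat dose 6 or 13. The interval of repeat dose 7 or 14 has no trough in the model, although its end-of-interval concentration is scheduled and participants are still in the unit. Neither document gives a reason for leaving it out.

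A trough taken after a dose is not foreign to the SAP. Section 8.2.4.1.1 lists Cτ among the Part A single-dose endpoints, where only a post-dose sample can supply it.

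What is at stake is the width of the interval around the reported slope. The 7-day cohort, added to study higher exposures, has four trough days over a 4-day span and about 9 active participants, so it has the least information to spare.

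**Working it through.** The documents state no SE or CI width for the slope, so there is no planned figure to reproduce.

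**1. Inputs.** Trough days come from SAP 8.2.4.1.2, last-dose days from Protocol 4.1, the 24 h sample from Protocol 1.3, and 9 active participants per cohort from Protocol 9.2. Once-daily dosing is assumed in steps 2 to 5.

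**2. Formula.** With a participant intercept, independent residuals and complete data, SE(slope) = σ / √(n·Sxx), where Sxx is the sum of squared deviations of day from its mean. The width ratio without versus with the extra day is √(Sxx with / Sxx without). It does not depend on σ or n.

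- 7-day, Days 6, 7, 9, 10: mean 8, Sxx = 4 + 1 + 1 + 4 = 10.0. Adding Day 11: mean 8.6, Sxx = 6.76 + 2.56 + 0.16 + 1.96 + 5.76 = 17.2. Ratio √(17.2/10.0) = 1.311.
- 14-day, Days 6, 7, 9, 10, 11, 15, 16, 17: Sxx = 1157 − 91²/8 = 121.875. Adding Day 18: 1481 − 109²/9 = 160.889. Ratio √(160.889/121.875) = 1.149.
- Protocol 9.4's shorter example for 14-day dosing (Days 6, 7, 16, 17): 101.0 rises to 134.8, ratio 1.155.

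Including the t quantiles (n = 9; df 26 versus 35, and 62 versus 71) gives 1.324 and 1.151.

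**3. Illustration.** The within-participant SD of log trough is not in the documents. I assume 0.2, range 0.15 to 0.3, with n = 9. The half-width is 100·(exp(t·SE) − 1) % per day.

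| Cohort | SD 0.15 | SD 0.2 | SD 0.3 |
|---|---|---|---|
| 7-day | 2.7 to 2.1 | 3.7 to 2.8 | 5.5 to 4.2 |
| 14-day | 0.76 to 0.66 | 1.01 to 0.88 | 1.52 to 1.32 |

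Each cell runs from the planned analysis to the one with the added sample.

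**4. Sensitivity to the covariance model (generalised least squares).**

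| Model | 7-day | 14-day |
|---|---|---|
| Random intercept, independent residuals | 1.311 | 1.149 |
| Random slope, variance σ²/Sxx | 1.125 | 1.067 |
| Random slope, variance 3σ²/Sxx | 1.057 | 1.032 |
| AR(1) residuals, ρ = 0.6 | 1.219 | 1.106 |

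**5. Does it help to detect residual accumulation?** I computed expected log troughs from a one-compartment model with doses on Day 1 and daily from Day 4, at the half-life of about 13 h in SAP 13.4.1.

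- 7-day: the expected slope falls from 0.0170 to 0.0133 per day. Slope/SE changes by a factor (0.0133/0.0170) × 1.311 = 1.026, or +2.6%.
- 14-day: 0.00412 falls to 0.00357 per day. The factor is (0.00357/0.00412) × 1.149 = 0.996, or −0.4%.
- Over half-lives from 6.1 to 22 h, the change is −0.1% to +6.6% (7-day) and −0.9% to +0.5% (14-day).

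The late point sits on the plateau. It narrows the interval and flattens the line by nearly the same proportion.

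**6. Twice-daily dosing.** If the last dose is the morning dose, the 24 h sample lies 12 h past the end of its interval. At 13 h it is lower by (12/13)·ln 2 = 0.640 on the log scale, about 47%. Adding it to flat troughs creates a slope of −0.640 × 2.4/17.2 = −0.089 per day (7-day), or −0.640 × 5.889/160.889 = −0.023 (14-day). The 7-day artefact is about seven times the SE of 0.0121 at SD 0.15 (0.15/√(9 × 17.2)). The 12 h sample would be the true trough; leaving it out gives ratios of 1.22 (7-day) and 1.13 (14-day).

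**The case against.** The strongest reply is that a narrower CI does not mean a better answer on steady state. Information about residual accumulation lies in the early troughs, and step 5 shows that the added point leaves slope/SE almost unchanged. That stands. The full benefit arises only for a persistent linear drift, or when the slope and its interval are read as showing how flat the troughs are.

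Three further points stand:

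- The value is not wasted. Under once-daily dosing it enters the last-dose AUC(0-τ), and so Ro and Rss, and Protocol 9.4 also ties steady state to Rss.
- Both documents define the trough as pre-dose. Adding a post-dose value therefore departs from the protocol's secondary endpoint wording.
- No hypothesis is tested, no margin is set, and Protocol 9.2 says the sample size has no statistical basis. No formal decision turns on the width.

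The size is also conditional. The power-model boxes specify an intercept-only participant effect. The steady-state box says only that participant is random, with an unstructured G matrix, so a random slope is possible and the gain would then be smaller.

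A reader might infer that the planned slope is biased or invalid, or that the 24 h sample should simply be added in every cohort. The documents support neither. The analysis follows the protocol's own definition, and because the regimen is left open, an unconditional addition could create a false downward slope under twice-daily dosing.

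**Conclusion.** The point holds as an avoidable loss of precision in a valid analysis. Under once-daily dosing, with a participant intercept, independent residuals and complete data, the planned 90% CI for the slope is about 31% wider (7-day) and 15% wider (14-day) than the scheduled samples allow. With random slopes of variance σ²/Sxx the loss is about 12–13% and 7%, and with AR(1) residuals at ρ = 0.6 about 22% and 11%, so 31% and 15% are upper figures among the models checked.

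The gain is in ruling out drift, and power to detect residual early accumulation barely changes. It matters most for the 7-day cohort. It is worth making because the samples already exist, provided the added value is tied to the regimen actually used.

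**What to change.** - In SAP Table 2 and the steady-state box of 8.2.4.1.2, define Cτ as the concentration at the end of each dosing interval.
- Add the end-of-interval value after the last dose to the trough plot and slope model only where it is a true trough. For once-daily cohorts this is the 24 h sample (Day 11 or Day 18). For twice-daily cohorts it is the sample at the end of the last 12 h interval.
- Record this in SAP Table 1 as a change from the protocol's pre-dose definition.
- Keep the pre-dose-only slope as a sensitivity analysis, so that the protocol-defined result is still reported.

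The cost is SAP wording, a small documented departure from the protocol endpoint, and one extra model run. No new sample, assay or visit is needed.
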